1.1 Synopsis

Title: Comparing teaching before vs after simulation education on pediatric status epileptics: A randomized controlled trial

Study Description: The study will test whether simulation preceding didactic teaching leads to improved knowledge and performance retention compared to a didactic lecture preceding simulation. Participants will be randomized to one of two different groups: 1) didactic teaching followed by simulation or 2) simulation then didactic teaching.

Primary Outcomes:

1. Resuscitation performance retention score 3 months post-initial training

Secondary Outcomes:

2. Knowledge assessment 3 months post-initial training
3. Learner satisfaction

Hypothesis:

1. Didactic teaching after simulation-based training will be more effective in maintaining retention of knowledge and skills in the management of pediatric status epilepticus compared to didactic teaching prior to simulation

Study Population: Second year medical students from the University of British Columbia – Vancouver Campus

Description of Sites: The intervention will take place at BC Children’s Hospital Simulation Centre with trained facilitators and high-realism simulation equipment.

Description of Study Intervention: One arm of the study will receive a 60-minute lecture on pediatric status epilepticus management and then complete a simulation scenario immediately after. The second arm will complete a simulation scenario on pediatric status epilepticus without knowing the topic beforehand and will complete a 60-minute lecture immediately after the simulation session. Both groups will complete a knowledge test directly after the intervention. Both groups will be reassessed in three months with a repeat simulation scenario on pediatric status epilepticus and repeat knowledge test.

Study Duration The study will enroll participants for 2 months and then complete the educational intervention over 3 months.

Participant Duration: The participants will participate in one 60-minute lecture and two ten-minute simulation sessions and one focused 15 minute debrief over the course of four months’ time.

1.2 Schema:

[figure not shown]

Figure 1: Flow of participants through the research project

2 Introduction

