3.1 Outcome Measures

The primary outcome will be the resuscitation performance retention assessed using the post-teaching the final global rating scale score (1-7 performance score) for medical management and flow during each simulation as well as the following “time-to” metrics; glucose check, IV access, chemistry panel order, first-line anti-epileptic administration³⁰, second line anti-epileptic administration. This will be adjusted for baseline score.

The secondary outcome measures for knowledge retention assessment will be the post-teaching knowledge test score assessed on a 15 Question MCQ test administered at the final assessment adjusted for the baseline score.

Comfort/Confidence will be assessed using the change in Likert scale item after each simulation and debrief.

4 Study Population

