4.2 Expected Duration of Subject Participation

A participant will already be expected to attend a 60 min teaching session on status epilepticus. They will also be required to participate in two 10-25 min simulation sessions which will include a 10-minute simulation and 15 debrief for the first and only a 10-minute simulation the second time.

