5.2 Data Collection

The simulation sessions will be recorded to ensure accuracy in time to intervention recordings and global rating scales. Two experienced pediatric acute care specialists with simulation experience masked from the intervention arms will review the videos and determine the global rating scale for each simulation and they will review videos for the "time to metrics". Time zero will be immediately after the scenario description is completed.

The knowledge tests and anxiety/confidence assessment will be completed using a redcap-hosted survey. Basic demographic information including age, previous experience with simulation and a background in ED nursing or EMS will also be collected using a demographic survey. The names and contact information will not linked to the demographic or simulation information. This survey can be found in appendix A.

5.3 Didactic Lecture and Simulation Development:

The lecture and two simulation scenarios were developed by the primary researcher, a first-year pediatric emergency medicine fellow with guidance from the principal investigators, a pediatric intensivist and pediatric emergency medicine specialist who both have expertise in simulation and curriculum development. Both the lecture and simulations were peer-reviewed by a pediatric emergency medicine specialist with simulation expertise who was not involved with research project.

The lecture was developed using existing pediatric seizure management guidelines from Trekk and the Canadian Pediatric Society^{28,29}. The lecture learning objectives mirrored the research outcome measures and focused on acute management of pediatric seizures with supporting discussions on possible etiologies. It did not discuss crisis-resource management skills, long-term management or prognosis of seizures or other acute pediatric scenarios. The lecture can be found in PDF form in Appendix B.

The simulation scenarios were developed using published pediatric seizure scenarios as a baseline and set at a level appropriate for trainees with limited clinical experience. The pediatric status epilepticus scenarios can be found in appendix C.

5.4 Study Protocol:

The participants will be randomized into two groups: Lecture-> Simulation -> Evaluation Simulation(LS) and Simulation->Lecture -> Evaluation Simulation (SL) using blocked randomization with varied block size. The randomization allocation sequence will be completed by RedCap and the researchers will be masked to this.

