The LS group will complete the 60-minute focused lecture immediately prior to their initial simulation. The SL group will complete the 60-minute focused lecture immediately after their initial simulation. The LS group will complete a pre-intervention knowledge test prior to the lecture and the SL group will complete a knowledge test prior to the initial simulation.

Both groups will complete the initial simulation in groups of 3-4 with one member acting as the leader and others acting as team members. The simulation will last for 10 minutes followed by a structure debrief using the +/-delta method lasting up to 20 minutes. The debrief will be completed by a pediatric emergency medicine specialist with experience in leading simulation debrief. The leader of the group will be recorded for later subgroup analysis.

Every individual will complete a second evaluatory simulation 3 months after the initial simulation to evaluate the primary outcome of resuscitation performance retention. Each participant will act as the simulation leader with two actors who will function as a highly trained nurse and second physician but will not provide advice. The simulation will be videotaped. The participants will also complete a knowledge test prior after the second simulation.

Simulation videos will be reviewed as per the above data collection method to determine outcome measures. The simulations will be completed in the BCCH simulation center with a trained pediatric simulation expert and simulation facilitator. A high-fidelity mannequin will be used. It can seize and has appreciable chest rise and breath sounds. The participants will be instructed to assume all medications requested are drawn up in a syringe to the dose desired in the medication tray to decrease variability in time to metrics from difficulty in drawing up medications.

6 Statistical Consideration

6.1 Sample Size Determination:

The one paper assessing knowledge and skill retention comparing SL and LS structured teaching found a 13.42% difference in skill performance on transesophageal echocardiography²⁴ with the following means and std; LS group 71.90 (18.59) and SL group 85.32(15.63). Using a sample size calculator estimates a sample size of 60 with an alpha of 0.05 and power of 0.8³¹.

6.2 Statistical Analysis:

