31. Kane S. Sample Size Calculator. ClinCalc.com. Published July 24, 2019. Accessed October 17, 2022. <https://clincalc.com/stats/samplesize.aspx>

**Appendix A:
Demographics:**

Please enter your age:

What is your experience with medical simulation?

a) No experience b) 1-5 simulation experiences c) 5-10 simulation experiences d) >10 simulation experiences

Before entering medicine please check any roles that apply?

- Background in ED Nursing
- Background as a paramedic or first responder?

Confidence Quiz:

Please rate your anxiety in the simulation experience from 1 to 5?

1 – Extremely anxious 5 – Not anxious at all

Please rate your confidence in managing pediatric seizures in the future?

1 – Not confident at all, 5 – extremely confident

Please rate your satisfaction with the educational experience (Simulation + Debrief + Lecture)?

1 – extremely dissatisfied , 5 extremely satisfied

Initial priorities

- Cardiorespiratory monitor, BP and temp
- Point of care glucose
- 100% oxygen via non-rebreather mask
- IV access
- Tylenol
- Primary survey
- Initial anti-seizure medication

Powered by **Dall E Everywhere**

Stabilization

Initial Management

- Initiate ABCs, cardiorespiratory and BP monitoring
- O₂ 10-15 L/min via non-rebreather mask
- Prioritize giving the first dose of benzodiazepine as early as possible, followed by checking blood glucose
- Monitor for respiratory depression, hypotension, arrhythmias
- Give acetaminophen 15 mg/kg/dose (MAX 650 mg) PR if febrile
- Consider other investigations:**
 - Electrolytes, blood gas, calcium, CBC, serum glucose
 - Other: anticonvulsant drug levels, LFTs, blood & urine culture

Primary Survey – A - Airway

Recognize	Assess for	Manage
A Airway Obstruction	
 Position (hyper/hypo extension) Patency (Blood, Vomiting) Need for protection 	
 Oral Suction Sniffing Position Oral Airway Jaw thrust Bag-mask ventilation

Primary Survey – B - Breathing

Recognize	Assess for	Manage

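### Read literally, the change in confidence compares a post-lecture first rating in one arm with a pre-lecture first rating in the other; fix the timing and compare the final rating

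*Combined protocol and SAP*

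**What the plan says.** - **Measure and timing (3.1 Outcome Measures):** "Comfort/Confidence will be assessed using the change in Likert scale item after each simulation and debrief". No other sentence ties this measure to a time point, and the direction of the change is not defined.
- **Order of events (5.4 Study Protocol):** "The LS group will complete the 60-minute focused lecture immediately prior to their initial simulation". For the other arm: "The SL group will complete the 60-minute focused lecture immediately after their initial simulation". In both arms the debrief follows the first simulation.
- **Objective (Section 3):** the aim is learners' comfort in the initial simulation, with no second time point and no change.
- **Instrument (Appendix A, Confidence Quiz):** anxiety, confidence and satisfaction are each rated 1 to 5 under one heading. The satisfaction item reads "Please rate your satisfaction with the educational experience (Simulation + Debrief + Lecture" and closes the bracket there. The Synopsis lists "Learner satisfaction" as a secondary outcome.
- **Second session (4.2):** "only a 10-minute simulation the second time", so no debrief is described there.
- **Administration (5.2):** "The knowledge tests and anxiety/confidence assessment will be completed using a redcap-hosted survey", with no time given.
- **Analysis (6.2):** secondary Likert outcomes go into a proportional odds model. The section does not say whether the final rating, the change or an adjusted rating is modelled.

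**The concern.** The trial gives both arms the same content and asks whether order matters. A fair comparison of change needs first ratings taken at equivalent points. If staff follow 3.1 to the letter, the two first ratings fall on opposite sides of the lecture: LS rates confidence with the lecture behind it, SL with the lecture still to come. Any boost from the lecture then sits in the starting value for LS and in the gain for SL.

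A report could therefore show a larger gain in confidence for SL, the arm the hypothesis favours, that reflects only when the form was handed out. The same artefact could hide a true disadvantage of SL. On this timing SL students would also be asked to rate satisfaction with a lecture they had not yet attended.

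**Working it through.** The plan gives no effect size, SD or power for confidence, so there is no figure of its own to reproduce. The check is the event order, then algebra, then an illustration.

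**1. Event order on the literal reading of 3.1 with 5.4**

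- LS: lecture, simulation 1, debrief, **rating 1**, about 3 months, simulation 2, **rating 2**.
- SL: simulation 1, debrief, **rating 1**, lecture, about 3 months, simulation 2, **rating 2**.

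**2. Algebra.** Take change as rating 2 minus rating 1 (the natural reading, not a stated definition). All contrasts are SL minus LS. Let O be the order effect on the final rating, O1 the order effect at the end of the first session, and L the effect of the lecture on the first rating.

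| Analysis | Rating 1 contrast | Rating 2 contrast | Contrast analysed |
|---|---|---|---|
| Change, literal timing | -L | O | O - (-L) = O + L |
| Change, end-of-session timing | O1 | O | O - O1 |
| Final rating alone, either timing | not used | O | O |

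With O = 0, literal timing returns L. With end-of-session timing the lecture term is gone, but a lasting order effect (O1 = O) gives O - O1 = 0, so the change cannot show it. Adjusting for rating 1 does not repair literal timing, because rating 1 is taken after randomisation and already depends on arm. No confidence rating before the intervention is described.

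**3. Illustration of size (effects and SDs assumed).** Take 30 per arm (the 60 of Section 6.1, split equally), O = 0, and a two-sided 5% test. The standard error of the difference in mean change is SD × √(2/30) = 0.258 × SD. The rejection rate is Φ(L/SE - 1.96) + Φ(-L/SE - 1.96). For L = 0.5 and SD = 1.0, L/SE = 0.5/0.258 = 1.94 and the rate is 49%.

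| L (points) | SD of change 0.8 | 1.0 | 1.2 |
|---|---|---|---|
| 0 | 5% | 5% | 5% |
| 0.25 | 23% | 16% | 13% |
| 0.5 | 68% | 49% | 37% |
| 1.0 | 99.8% | 97% | 90% |

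**4. Cross-check with the planned type of model.** Ratings were simulated as rounded normal values from 1 to 5 (first mean 2.5, final mean 3.2; latent SD/correlation 0.8/0.6, 0.9/0.5 and 1.0/0.4; 2,000 trials per setting) and tested with a proportional odds model:

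- Literal timing, no order effect, change score: 4-5% at L = 0, 12-20% at 0.25, 37-65% at 0.5, 91-99.5% at 1.0. The final rating alone stayed at 5-6%.
- End-of-session timing, L = 0.5, no order effect, change score: 5-6%.
- End-of-session timing, order effect of 0.5 at both ratings: change 5-6%, final rating 44-60%.
- Literal timing, L = 0.5, SL truly worse by 0.5: change 4-5%, final rating 44-63%.

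**The case against.** The strongest reply is that 3.1 says after, not immediately after. A form completed at the end of the first session is also after the simulation and debrief. The satisfaction item covers simulation, debrief and lecture together, so an SL student could not sensibly answer it before the lecture. That favours one end-of-session form, under which the lecture bias does not arise. In addition, 6.2 never says that raw change will be tested between arms. Both points stand, and they make the bias conditional.

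They do not settle the matter. The end-of-session timing is inferred from the wording of one item, while 3.1 attaches the confidence rating to the simulation and debrief and names change as the measure. Staff could follow either in good faith.

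A reader might also infer that the passages flatly contradict one another on when the quiz is given. The documents do not support that. The Synopsis sentence "Both groups will complete a knowledge test directly after the intervention" concerns the knowledge test only, and 5.2 is silent on timing. Most of this is under-specification. The missing second debrief is a small mismatch, since 3.1 may mean each simulation and its debrief where there is one. The clearer tension is between Section 3 (comfort in the first simulation only) and 3.1 (change across two ratings).

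Finally, it can be said that change is a legitimate measure of retention, which is the trial's theme. That is fair once the timing is equal, and it is a reason to keep change as a secondary description.

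**Conclusion.** The point holds conditionally and is minor. On the literal timing, the between-arm difference in change is O + L and does not isolate order. On end-of-session timing it is O - O1: free of the lecture effect, but blind to an order effect that lasts. The final rating gives O on both.

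The direction of the bias rests on the lecture raising confidence, which is plausible but not shown in the documents. Its size cannot be derived from them, and the rejection rates above only show what assumed lecture effects would do. A reader might infer that the planned confidence result is certainly biased, or that the trial's main result is in doubt. Neither follows: the wording allows an unbiased schedule, and the primary outcome, the knowledge results and a comparison of final confidence ratings are untouched. What is exposed is the change in confidence and, on the literal timing, the meaning of the SL satisfaction score.

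**What to change.** 1. In 3.1 and 5.4, state that the confidence and satisfaction items are given in both arms at the end of the whole first session, with lecture, simulation and debrief all done, and that confidence is rated again after the second simulation. Drop the implication of a second debrief.
2. In 6.2, name the between-arm comparison of the final confidence rating, by the proportional odds model already planned, as the main confidence analysis. Keep the change from end of session to final rating, defined as second minus first, as a secondary description of retention.
3. Reconcile Section 3 with 3.1 by reporting comfort or anxiety in the initial simulation as a level at session 1, not as a change.

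The cost is wording, plus a shift of the quiz by at most about an hour in SL (the 60-minute lecture). LS timing does not move, and no visit or item is added. If end-of-session timing was always intended, only the text changes. If first ratings have already been collected, the final-rating comparison remains usable on either timing, and the report should say when the first rating was taken in each arm.

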4.1 Inclusion Criteria

1. Second year medical students at the University of British Columbia – Vancouver Campus

4.2 Expected Duration of Subject Participation

A participant will already be expected to attend a 60 min teaching session on status epilepticus. They will also be required to participate in two 10-25 min simulation sessions which will include a 10-minute simulation and 15 debrief for the first and only a 10-minute simulation the second time.

4.3 Recruitment and Retention

The study participants will be recruited from the second-year medical student cohort at the University of British Columbia Vancouver campus. A medical student assisting in the research project will be the primary point for recruiting medical students and will post regularly in medical student communication channels including but not limited to Slack, Facebook and word of mouth. The participants names and contact information will be saved at this stage to allow for scheduling of the simulation and teaching sessions.

The consent form will be emailed to participants to complete prior to participation and researchers will be available for questions.

5 Study Design

5.1 Overall Design

This is a parallel randomized control trial in medical education that will be conducted at the BC Children's Hospital. The participants will be masked to the other arm of the intervention and the outcome measures of the study.

5.2 Data Collection

The simulation sessions will be recorded to ensure accuracy in time to intervention recordings and global rating scales. Two experienced pediatric acute care specialists with simulation experience masked from the intervention arms will review the videos and determine the global rating scale for each simulation and they will review videos for the "time to metrics". Time zero will be immediately after the scenario description is completed.

The knowledge tests and anxiety/confidence assessment will be completed using a redcap-hosted survey. Basic demographic information including age, previous experience with simulation and a background in ED nursing or EMS will also be collected using a demographic survey. The names and contact information will not linked to the demographic or simulation information. This survey can be found in appendix A.

5.3 Didactic Lecture and Simulation Development:

The lecture and two simulation scenarios were developed by the primary researcher, a first-year pediatric emergency medicine fellow with guidance from the principal investigators, a pediatric intensivist and pediatric emergency medicine specialist who both have expertise in simulation and curriculum development. Both the lecture and simulations were peer-reviewed by a pediatric emergency medicine specialist with simulation expertise who was not involved with research project.

The lecture was developed using existing pediatric seizure management guidelines from Trekk and the Canadian Pediatric Society^{28,29}. The lecture learning objectives mirrored the research outcome measures and focused on acute management of pediatric seizures with supporting discussions on possible etiologies. It did not discuss crisis-resource management skills, long-term management or prognosis of seizures or other acute pediatric scenarios. The lecture can be found in PDF form in Appendix B.

The simulation scenarios were developed using published pediatric seizure scenarios as a baseline and set at a level appropriate for trainees with limited clinical experience. The pediatric status epilepticus scenarios can be found in appendix C.

5.4 Study Protocol:

The participants will be randomized into two groups: Lecture-> Simulation -> Evaluation Simulation(LS) and Simulation->Lecture -> Evaluation Simulation (SL) using blocked randomization with varied block size. The randomization allocation sequence will be completed by RedCap and the researchers will be masked to this.

The LS group will complete the 60-minute focused lecture immediately prior to their initial simulation. The SL group will complete the 60-minute focused lecture immediately after their initial simulation. The LS group will complete a pre-intervention knowledge test prior to the lecture and the SL group will complete a knowledge test prior to the initial simulation.

Both groups will complete the initial simulation in groups of 3-4 with one member acting as the leader and others acting as team members. The simulation will last for 10 minutes followed by a structure debrief using the +/-delta method lasting up to 20 minutes. The debrief will be completed by a pediatric emergency medicine specialist with experience in leading simulation debrief. The leader of the group will be recorded for later subgroup analysis.

Every individual will complete a second evaluatory simulation 3 months after the initial simulation to evaluate the primary outcome of resuscitation performance retention. Each participant will act as the simulation leader with two actors who will function as a highly trained nurse and second physician but will not provide advice. The simulation will be videotaped. The participants will also complete a knowledge test prior after the second simulation.

Simulation videos will be reviewed as per the above data collection method to determine outcome measures. The simulations will be completed in the BCCH simulation center with a trained pediatric simulation expert and simulation facilitator. A high-fidelity mannequin will be used. It can seize and has appreciable chest rise and breath sounds. The participants will be instructed to assume all medications requested are drawn up in a syringe to the dose desired in the medication tray to decrease variability in time to metrics from difficulty in drawing up medications.

6 Statistical Consideration

6.1 Sample Size Determination:

The one paper assessing knowledge and skill retention comparing SL and LS structured teaching found a 13.42% difference in skill performance on transesophageal echocardiography²⁴ with the following means and std; LS group 71.90 (18.59) and SL group 85.32(15.63). Using a sample size calculator estimates a sample size of 60 with an alpha of 0.05 and power of 0.8³¹.

6.2 Statistical Analysis:

The recorded simulation sessions will be reviewed by two separate pediatric emergency medicine and simulation experts who will evaluate the participants on the simulation global rating scale, a validated assessment tool for simulation. Inter-rater reliability will be calculated via Pearson correlation and ICC statistics, and the final reported value will be the mean of both reviewers.

The recorded sessions will also be reviewed to the time to metrics by two reviewers with a masked co-investigator serving as the tie breaker in times of significant discordance. Time zero for the “time to” metrics will be when the facilitator finishes the scenario description.

The mean and 95% confidence interval of the metrics will be calculated for each group. Post randomization scores will be compared using a paired t-test, and with mixed effects linear models using pre-randomization score as a covariate. Time-to-event measures will be displayed with Kaplan Meier graphs and median time, and tested with the log-rank test, and secondarily using Cox proportional hazards models. Regression models may include adjustment for baseline variables imbalanced between arms or prognostic of outcome. Secondary Likert outcomes will be assessed with a proportional odds model. All results will be presented with appropriate 95% confidence intervals. Statistical analysis will be completed with statistician support using R statistical software.

Protocol Deviations:

All deviations will be reported to the REB in a timely manner.

7 Data Handling and Record Keeping:

7.1 Data Management Responsibilities:

The data will be stored on a secure redcap data-server. The server will be password protected and only the research team will have access to the data. Participant data will only be stored de-identified. The video recordings will be stored on an encrypted external hard drive kept in the PI's office locked office in a locked drawer. The original video data would be deleted from the simulation center.

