2.2.2 Known Potential Benefits

The participants will benefit from two simulation teaching sessions with a trained simulation expert and FRPC certified pediatric emergency medicine physician. They will also receive an additional lecture providing them with didactic teaching on status epilepticus.

3 Objectives

The primary objective is to assess the resuscitation performance retention difference between the two educational intervention arms at two to four months following teaching.

The secondary objectives are to assess the difference in knowledge between both study groups immediately after and two to four months after the educational intervention. In addition, we will measure the comfort of learners performing the initial simulation scenario.

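### Section 6.2 specifies a paired t-test for the score outcomes of a parallel two-arm trial that has no pairs

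*Combined protocol and SAP*

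**What the plan says.** On the score outcomes, section 6.2 (Statistical Analysis) reads "Post randomization scores will be compared using a paired t-test", and continues "and with mixed effects linear models using pre-randomization score as a covariate". It does not say which of the two is primary. The time-to metrics are handled separately and in a stated order: "tested with the log-rank test, and secondarily using Cox proportional hazards models".

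The design sections describe unpaired groups. Section 5.1: "This is a parallel randomized control trial in medical education". Section 5.4 allocates students to LS or SL "using blocked randomization with varied block size", and mentions no matching and no crossover. Section 3 sets the target: "The primary objective is to assess the resuscitation performance retention difference between the two educational intervention arms".

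Section 3.1 says of the primary outcome, which includes the 1-7 global rating scale: "This will be adjusted for baseline score". The only score that section 5.4 places before any teaching is the knowledge test. For LS, "The LS group will complete a pre-intervention knowledge test prior to the lecture"; the SL group takes its test before the initial simulation.

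**The concern.** A paired t-test needs each observation to have a natural partner. Here no LS student is linked to an SL student, and blocks of varied size do not create such links. Two readings remain:

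- **Across arms.** Someone must invent the pairs. The result then depends on the pairing, and students are left out whenever the arms differ in size.
- **Within student**, for example the knowledge test straight after the session against the one at three months. This can be computed and describes decay, but it does not compare LS with SL.

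Pairing the two raters is not a third reading, because section 6.2 averages them into one value.

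At stake is the arm comparison of the global rating scale, which is part of the primary outcome, and of the knowledge test. With t-test and model listed side by side and unranked, the choice of reported result stays open until the data have been seen.

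**Working it through.** **Inputs.** Section 6.1 gives LS 71.90 (SD 18.59), SL 85.32 (SD 15.63), alpha 0.05, power 0.80 and a sample size of 60. Assumed, because not stated: two-sided test, 1:1 allocation, 60 as the total. These planning values come from an echocardiography score in percent, not from the 1-7 scale.

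**1. The plan's own figure.** The difference is 85.32 − 71.90 = 13.42. For two independent means, n per arm = 2 × SD² × (1.960 + 0.842)² / 13.42².

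| SD used | n per arm | Total before rounding |
|---|---|---|
| 18.59 (LS) | 30.1 | 60.2 |
| 17.17 (pooled, √[(18.59² + 15.63²)/2]) | 25.7 | 51.4 |
| 15.63 (SL) | 21.3 | 42.6 |

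The LS SD reproduces 60 to within rounding (strict rounding up gives 31 per arm, 62 in total). The inputs are two separate arm means and SDs; no within-pair correlation or SD of differences is given.

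**2. Power lost by arbitrary pairing.** With 30 per arm the degrees of freedom fall from 58 to 29, and the critical t rises from 2.002 to 2.045. The noncentrality is the same for both tests, 13.42 / (SD × √(2/30)).

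| SD | Noncentrality | Independent, df 58 | Arbitrary pairs, df 29 |
|---|---|---|---|
| 17.17 | 3.03 | 84.5% | 83.3% |
| 18.59 | 2.80 | 78.5% | 77.1% |

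Simulated type I error with arbitrary pairs is 5.0% (200,000 trials).

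**3. Non-uniqueness of the p-value.** Twenty data sets were built with sample SDs 18.59 and 15.63 and a mean difference of 8.88, which gives a two-sample p of 0.050 (2.002 × 17.17 × √(2/30) = 8.88). Each was paired at random 20,000 times. On average, 95% of pairings gave p between 0.019 and 0.096, and 41% gave p below 0.05.

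Over whole trials (100,000 simulated for each row), two random pairings of the same data disagreed on significance this often:

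| True difference | Disagreement |
|---|---|
| 0 | 2.4% |
| 6.71 (half the planned effect) | 7.2% |
| 13.42 (planned effect) | 5.2% |

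**4. Unequal arms.** The documents give no loss rate. If 30 per arm are randomized and students drop out independently, the chance that both arms keep the same number is the sum of squared Binomial(30, 1 − loss) probabilities: 25%, 17%, 14% and 13% for assumed losses of 5%, 10%, 15% and 20%. Otherwise, pairing discards students.

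**5. The within-student reading.** As an illustration, assume both arms gain 0.5 SD between two tests, with correlation 0.5 and no arm difference. The SD of the change is then 1 SD, and a paired test in one arm of 30 has noncentrality 0.5 × √30 = 2.74. It rejects about 75% of the time, while the independent LS-versus-SL test rejects about 5% of the time. The two tests answer different questions.

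**6. Whether the mixed model repairs it.** The model asks for a score from before randomization. For the knowledge test, section 5.4 describes a score from before teaching. For the global rating scale there is none. The initial simulation takes place after allocation, follows the lecture in LS but precedes it in SL, and is run in groups of 3-4 with one leader. A rating from it can be affected by the intervention and is not an individual baseline.

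**The case against.** The strongest reply is that the valid analysis is already in the plan. Section 3.1 requires baseline adjustment, which a t-test cannot provide and the model can. Section 6.2 also speaks of adjusting for variables imbalanced between arms, which makes sense only if the models compare arms. On this view, paired is a slip for two-sample, or refers to decay within students, which section 2.1 names as an interest. The numerical damage is slight, and the wide p-value range arises because the example sits exactly at 0.05.

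Much of this stands. Section 3.1 does point towards the model, the slip is plausible, and the losses in step 2 are little more than one percentage point. But section 6.2 still prescribes the paired test without ranking it below the model, although its next sentence does rank log-rank and Cox. The within-student reading cannot serve the stated objective, and it is weakest for the global rating scale, where the first simulation is a group exercise. For that scale the model also lacks a described covariate.

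It is also fair to say that a Welch test treats students as independent although they train in groups of 3-4. Assuming an intraclass correlation of 0.05 and a mean group size of 3.5, the design effect is 1 + 2.5 × 0.05 = 1.125, and power falls from 84.5% to 80.1%, or from 78.5% to 73.6%. That exceeds the loss from pairing, but it is a separate matter and does not make the paired test right.

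Finally, 60 does not by itself rule out a paired calculation, since a paired formula with zero correlation gives the same number. The case rests on the design, not on the sample size.

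**Conclusion.** The point holds and should be fixed. As written, the t-test on the score outcomes is either undefined (across arms) or aimed at a different quantity (within students), and no other section corrects it. This follows from the design alone.

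The size is modest: about 1.2 to 1.4 percentage points of power, no inflation of type I error, and a conclusion that changes with the pairing in 2.4% to 7.2% of trials. These figures assume 30 per arm, a two-sided test and the planning SDs from section 6.1. The greater weakness is that neither the t-test nor the model is named as primary, and the model's baseline is not described for the global rating scale. The time-to metrics are unaffected.

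**What to change.** In section 6.2:

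- Replace the paired t-test with an independent two-sample (Welch) t-test of LS against SL, as the unadjusted supporting analysis.
- State that the regression (mixed) model for each score contains a randomized-arm term, reports the SL − LS difference with its 95% confidence interval, and is the primary analysis of that score.
- Adjust only for values that precede any teaching: the pre-intervention knowledge test and the demographics already collected, such as previous simulation experience.
- Label any within-student paired test as descriptive.
- Leave the log-rank and Cox analyses as planned.

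In section 3.1, say what the baseline score means for the global rating scale, consistent with the third item. If the authors meant a rating from the initial simulation, they should recognize that it follows allocation and should not use it as a baseline covariate.

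The cost is about two sentences in 6.2 and one clarification in 3.1. Nothing changes operationally, and this correction leaves the sample size of 60 essentially unchanged, because the independent-means calculation already yields it.
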